[figure not shown]

[figure not shown]
**A Research on the Clinical Significance of Sentinel Lymph Node
Imaging Combined With Imaging Examination in Pelvic and
Peritoneal Lymphadenectomy for Endometrial Carcinoma**

2019.02.01

Study objectives The primary objective of this study is to identify the specific number and percentage of pelvic and abdominal lymph nodes that are invaded by metastatic endometrial carcinoma, and to calculate the coincidence rate of lymph node imaging and pathological examination. By setting up the control group and experimental group, we plan to find out whether pelvic and abdominal lymphadenectomy would exert positive effect on patients with endometrial carcinoma.

Trial design This is a prospective interventional trial. After signing of informed consent, the electronic medical data of patients with endometrial carcinoma will be collected in this study. The specific number and percentage of pelvic and abdominal nodes that are invaded by tumor cells will be calculated. By combining the imaging results and pathological test, we plan to obtain the coincidence rate of three tests. Finally, we would randomize patients into the control group and the experimental group as to receive the pelvic and peritoneal lymphadenectomy. When their postoperative data such as the reoccurrence rate and the five year survival rate are compared, the effect of pelvic and peritoneal lymphadenectomy on the prognosis of endometrial carcinoma are drawn.

Sample size The planned sample size was based on data from a previous study, in which the standard deviation was 5. We assumed an one-tailed α error of 0.05 and a sampling error of 1.0. We propose to enroll 70 participants including 35 patients in the control group and the others in the experimental group, and allow for a dropout rate of 10% for an effective sample size of 60.

Inclusion criteria

1. Volunteer to participate in the study with informed consent;
2. Females aged 10-90 who are confirmed with endometrial carcinoma and are willing to receive primary non-reserved fertility function surgery.

Exclusion criteria

1. Pregnancy, lactation, postmenopause, or planned pregnancy within two years;
2. Suspected or identified as other tumors of genital tract;
3. History of hyperparathyroidism, infectious diseases (tuberculosis, AIDS), autoimmune diseases, or digestive system diseases (malabsorption, crohn disease and dysentery);
4. Other diseases or heavy injuries that will interfere with the results;

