5. Simultaneous participation in another clinical study with investigational medicinal product(s) or researcher thinks the subjects are not suitable for this trial.

Withdrawal Subjects must be withdrawn from the study when one of the following criteria occurs:

1. At their own request. At any time during the study and without giving reasons, a subject may decline to participate further. The subject will not suffer any disadvantages as a result;
2. In the investigator's opinion, continuation of the study treatment would be harmful to the subject's health;
3. Obvious non-compliance;

4. Lost to follow-up;
5. Pregnancy;
6. Other medical or surgical treatments of endometrial carcinoma.

Safety assessments

Safety will be assessed by renal and liver function test, electrolyte, routine blood test. Other indicators are detected during the operation and rehabilitation period. The occurrence of any adverse events in participants will be recorded in the case report forms during each patient visit. We will withdraw patients who have severe adverse events, as it is unsafe for them to continue the trial. Meanwhile, we will give them relevant medical care and follow them up until the reaction has terminated.

Statistic analysis

The specific number and percentage of pelvic and abdominal lymph nodes that are invaded by tumor cells are collected. Multiple linear regression analysis was applied to evaluate the risk of lymphatic metastasis related to fourteen independent variables including four qualitative variables (hypertension, diabetes, diagnosis according to the FIGO staging system and the pathological tumor type) and eight quantitative variables (age, BMI, the number of lymph nodes, the interval between biopsy and operation, surgical time, surgical bleeding, postoperative anticoagulant time, preoperative value of Hb, preoperative value of RBC and preoperative value of Hct). All statistical analyses were performed by SPSS 17.0 software package and the level of statistical significance was set at $P < 0.05$. All independent variables were incorporated into the model using the method of "Enter". Data are presented as mean \pm standard deviation. Meanwhile, we collect the lymph node imaging results and the pathological test results so as to investigate the coincidence rate of the three examinations by chi test. As to the analysis of the lymphadenectomy on patients, we would conduct corresponding statistical method to interpret the follow-up data.

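### The randomised prognosis conclusion has no decisive outcome: recurrence, five-year survival and an open list of others share P < 0.05 with no multiplicity control, so the false-positive rate exceeds 5% if any one may carry the claim

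*Combined protocol and SAP*

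**What the plan says.** All references are to the combined protocol and SAP.

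- **Study objectives.** The stated primary objective is the number and percentage of invaded nodes and the agreement of imaging with pathology. The control and experimental groups serve a further question: to "find out whether pelvic and abdominal lymphadenectomy would exert positive effect on patients with endometrial carcinoma".
- **Trial design.** Randomisation is followed by a comparison of outcomes: "When their postoperative data such as the reoccurrence rate and the five year survival rate are compared". From this, "the effect of pelvic and peritoneal lymphadenectomy on the prognosis of endometrial carcinoma are drawn". Two outcomes are named as examples, and neither is ranked above the other.
- **Statistic analysis.** One threshold covers everything: "All statistical analyses were performed by SPSS 17.0 software package and the level of statistical significance was set at" P < 0.05. Sidedness is not given, no multiplicity adjustment is mentioned, and the method for the follow-up data is left to be chosen.
- **Sample size.** The only statement of sidedness is here: "We assumed an one-tailed α error of 0.05 and a sampling error of 1.0".

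**The concern.** The randomised comparison leads to a single conclusion about prognosis, but the plan allows at least two outcomes to feed it and leaves the list open. It does not say which outcome decides, whether one is enough, or whether all must agree. With about 30 evaluable patients per arm (the stated effective 60, halved), recurrence and five-year survival could easily give different answers. The choice of which to believe could then be made after the results are known, and 0.05 would no longer be the error rate of the conclusion.

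This is separate from the unspecified test for the follow-up data. Fixing a test for each outcome would still leave open which outcome settles the question.

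**Working it through.** **1. Does another part of the plan identify the decisive outcome?** The primary objective does not, since it concerns nodes and imaging agreement. The Sample size section was checked next. Its inputs are an SD of 5 ("The planned sample size was based on data from a previous study, in which the standard deviation was 5"), a one-tailed alpha of 0.05 and a sampling error of 1.0. A one-sample precision formula gives

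n = (z × SD / E)² = (1.645 × 5 / 1.0)² ≈ 67.6, rounded up to 68,

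which is close to the planned 70. A two-sided z gives 97 and does not match. So 70 appears to come from estimating one mean. The SD is tied to no named variable, and the calculation does not involve recurrence or survival. It does not settle which prognosis outcome decides.

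**2. Error rate if any one outcome may carry the claim.** With no true effect and each test at 0.05, one outcome gives 5%. For k independent outcomes the chance of at least one P < 0.05 is 1 − 0.95^k:

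- k = 2: 1 − 0.95² = 9.75%
- k = 3: 1 − 0.95³ = 14.3%

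Recurrence and survival in the same patients should be positively related, which lowers these values. The documents give no correlation, so a range was assumed. The correlated entries below come from simulating equally correlated normal test statistics (1,000,000 draws per setting).

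| Assumed correlation | Two outcomes, two-sided | Two outcomes, one-sided | Three outcomes, two-sided |
|---|---|---|---|
| 0 | 9.75% | 9.75% | 14.3% |
| 0.5 | 9.1% | 8.8% | 12.5% |
| 0.7 | 8.4% | 8.1% | 10.9% |
| 0.8 | 7.8% | 7.5% | 9.8% |
| 0.9 | 7.0% | 6.8% | 8.3% |

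**3. Check at the trial's own size.** Recurrence and death were simulated as linked yes/no outcomes with 30 per arm (400,000 trials per setting), each compared by a pooled z test. Assumed rates were recurrence 15% to 30%, death in 60% to 80% of those who recur and in 2% to 5% of those who do not. The implied correlation was 0.58 to 0.82. The chance of at least one P < 0.05 was 7.6% to 9.5%. In the setting that gave 9.5%, the single tests themselves ran slightly high, at 5.3% and 5.5%.

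**4. Error rate if both must be significant.** P(both) = 0.05 + 0.05 − P(at least one). At correlation 0.7 this is 0.10 − 0.084 = 1.6%; at 0.9 it is 0.10 − 0.070 = 3.0%.

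**5. False claims of benefit only, two-sided tests.** One test gives 2.5%. Two give 1 − 0.975² = 4.9% if independent and 4.2% at correlation 0.7.

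**6. Error rate after the fix.** One decisive outcome at 0.05 gives 5.0%. Two outcomes at 0.05 / 2 = 0.025 each give at most 5%.

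**The case against.** The strongest reply is that the plan never says one significant outcome is enough. That is correct. The inflation depends on an either-outcome rule inferred from silence, and under a both-outcomes rule the error is below 5%. But the reply confirms that no rule exists, and that absence is the defect.

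A reader might infer that the false-claim rate is at least double the stated 5%. The documents do not support that as a floor. For the two named outcomes, 9.75% requires independence, so with positively related outcomes it is a ceiling. Passing 10% needs additional outcomes; the open wording permits them, but none is named.

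Sidedness is also a fair objection. The objective is directional and the sample size is one-tailed, while the analysis threshold has no stated side. One-sided testing changes the figures little. Counting only false claims of benefit under two-sided tests gives lower absolute rates, but they still rise above the single-test 2.5%.

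A reader might extend the point to the fourteen-variable regression, where 1 − 0.95^14 = 51%. That figure should not be relied on. The regression concerns lymphatic metastasis, not the randomised comparison. Independence is implausible for haemoglobin, red-cell count and haematocrit. Fourteen variables are also not necessarily fourteen coefficients, since stage and tumour type may need several each.

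Finally, prognosis is not the stated primary objective. That limits the weight of the point, but prognosis remains the declared purpose of the two groups.

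**Conclusion.** The point holds in a limited form. The prognosis conclusion rests on an open, unranked list of outcomes at P < 0.05, with no decisive outcome and no multiplicity control. If either named outcome alone may support the claim, the false-positive rate is about 7% to 10% instead of 5%, and higher if the list is extended. The range rests on assumed correlations of 0.9 down to 0, and the check at 30 per arm rests on assumed event rates; neither is in the documents. The inflation is moderate. It should be corrected because the randomised question currently has no decision rule, and supplying one is cheap.

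**What to change.** Before any follow-up data are compared, add a statement along these lines to the Statistic analysis section:

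> The effect of lymphadenectomy on prognosis will be judged on one outcome [for example, recurrence or death from any cause, timed from randomisation], tested at 0.05 [sidedness stated]. Recurrence alone, five-year survival and all other outcomes are supportive and will be reported as estimates with 95% confidence intervals, without a significance claim.

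The composite is only an example and does not appear in the documents; the choice of outcome is the sponsor's. Whichever sidedness is chosen must be stated and reconciled with the one-tailed 0.05 in the Sample size section.

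If the sponsor wants both named outcomes to be able to support the claim, test each at 0.025, or use Holm (smaller P value against 0.025, then the larger against 0.05), and close the list.

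Label the fourteen-variable regression as exploratory.

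**Cost.** This is mostly wording, with no extra patients. The sponsor gives up unadjusted significance claims on the supporting outcomes. A time-to-event outcome also requires recurrence and death dates to be recorded. Naming a decisive outcome does not show that 70 patients are enough to test it, since the sample size was not built on recurrence or survival.

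### The sample-size inputs fit the precision of one pooled mean; they do not size the 35/35 comparison of recurrence and five-year survival, and 70, 10% and 60 need reconciling

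*Combined protocol and SAP*

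**What the plan says.** The Study objectives section labels as primary a descriptive aim: how many nodes are invaded, in what percentage, and how well imaging agrees with pathology. A separate sentence gives the purpose of having two groups: "we plan to find out whether pelvic and abdominal lymphadenectomy would exert positive effect on patients with endometrial carcinoma". The Trial design section says how that is to be answered: "When their postoperative data such as the reoccurrence rate and the five year survival rate are compared", then "the effect of pelvic and peritoneal lymphadenectomy on the prognosis of endometrial carcinoma are drawn".

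The Sample size section gives its basis in two sentences: "The planned sample size was based on data from a previous study, in which the standard deviation was 5" and "We assumed an one-tailed α error of 0.05 and a sampling error of 1.0". It then sets enrolment at 70, "including 35 patients in the control group and the others in the experimental group", and says the plan will "allow for a dropout rate of 10% for an effective sample size of 60". It does not name the variable with SD 5, the formula, a power, a recurrence or survival rate, or a difference between groups.

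On the analysis of the randomised comparison, the Statistic analysis section says only that "we would conduct corresponding statistical method to interpret the follow-up data".

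**The concern.** Recurrence and five-year survival are event outcomes. A calculation that sizes a comparison of them needs a rate in one group, a difference worth detecting and a power (or a target interval width). None of these is stated. An SD with a sampling error belongs to the estimation of a mean.

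Patients are nevertheless randomised to an operation, and the text promises a conclusion on its effect. If 70 was chosen for something else, the comparison may well be too imprecise to tell a useful benefit from none, and nothing in the plan stops a non-significant result from being reported as absence of effect.

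A smaller matter sits in the same section: enrolment, dropout and effective size do not obviously agree, and the stated precision may not hold at the effective size.

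**Working it through.** **Inputs from the Sample size section:** SD 5; sampling error E = 1.0; one-tailed alpha 0.05 (z = 1.645); 70 enrolled, 35 per group; dropout 10%; effective size 60.

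**1. Reproducing 70.** Precision of one mean: n = (z × SD / E)².
- One-tailed z: (1.645 × 5 / 1)² = 67.6, so 68.
- One-tailed t: the smallest n with t × 5/√n ≤ 1 is 70 (0.996 at 70, 1.004 at 69).
- Two-tailed z: (1.960 × 5 / 1)² = 96.04, so 97; no match.
- One-sample test with a difference of 1.0 and 80% power, one-sided: 155; no match.
- Two means differing by 1.0, 80% power, one-sided: 2 × (1.645 + 0.842)² × 25 = 309, or 310 per arm after rounding up from unrounded z values; no match.

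Of the readings tried, only the one-tailed precision of a single mean over all patients lands near 70, and it counts evaluable patients.

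**2. Dropout.**
- 70 × 0.90 = 63 in total.
- By arm: 35 × 0.90 = 31.5, rounded down to 31, so 62 in total.
- 60 of 70 is a loss of 1 − 60/70 = 14.3%.
- Working backwards: 60/0.90 = 66.7, so 67, or 68 with equal arms. Rounded up, that could become 70.

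**3. Sampling error at the evaluable number, if the one-mean formula was used.**

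| Evaluable n | by z | by t |
|---|---|---|
| 63 | 1.036 | 1.052 |
| 62 | 1.044 | 1.061 |
| 60 | 1.062 | 1.079 |

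**4. What the randomised comparison could show (illustration only).** The documents give no rates, so the five-year survival values below are assumed, with no censoring and 30 per arm. SE = √[(p₁(1−p₁) + p₂(1−p₂))/30]; power = Φ(difference/SE − z), with z = 1.645 one-sided or 1.960 two-sided at 0.05; half-width = 1.96 × SE. Worked case, 80% vs 90%: SE = √[(0.16 + 0.09)/30] = 0.0913; 0.10/0.0913 = 1.095; Φ(1.095 − 1.645) = 0.29.

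| Assumed survival | One-sided power | Two-sided power | 95% half-width (points) |
|---|---|---|---|
| 80% vs 85% | 13% | 7% | 19 |
| 80% vs 90% | 29% | 19% | 18 |
| 80% vs 95% | 56% | 44% | 16 |
| 75% vs 95% | 73% | 62% | 17 |

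None reaches 80%. With all 35 per arm retained, the most favourable row rises only to 79% one-sided and 69% two-sided.

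**The case against.** **The comparison is not the labelled primary objective.** This stands. A secondary comparison need not be powered, and leaving it unsized is not in itself an error. What remains is that no sentence calls it exploratory, while two sentences commit the plan to an answer from it.

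**The calculation may have been meant for the node count.** It may. A reader might infer that the sponsor applied the wrong formula to survival. The documents do not support that, because they never say which variable has SD 5. The supportable statement is that the comparison is unsized.

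**60 may be the target, not the result.** This is a fair reading: 60 inflated for 10% dropout is 67 or 68, and 35 per arm is a natural rounding up. A reader might call 60 a plain arithmetic error, but the text allows both readings. On either, the gap is 2 to 3 patients and errs on the cautious side.

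**Power figures rest on assumptions.** They do, and the result depends strongly on the assumed gain. A reader might also take 1.0 as a between-group difference in means and conclude that the plan has 21% power (5 × √(2/35) = 1.195; Φ(1/1.195 − 1.645) = 0.21) and needs 310 per arm. That is hypothetical: the plan calls 1.0 a sampling error and states no power. The core point, that the needed inputs are absent, requires no assumption.

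**Conclusion.** The concern holds in a limited form and should be fixed. The stated inputs give about 70 as the precision of one pooled mean and contain nothing that sizes a 35/35 comparison of recurrence and five-year survival. The promised conclusion on prognosis therefore has no stated basis in the sample size. Under assumed survival gains of 5 to 20 points, one-sided power at 30 per arm is 13% to 73%, and the interval would extend about 16 to 19 points either side of the estimate. These figures would change with other rates or with censoring.

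The inconsistency among 70, 10% and 60 is minor, and so is the precision shortfall (1.04 to 1.08 against 1.0), which applies only if the one-mean formula was used.

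A reader might go further and infer that the trial cannot meet its primary objective, or that 70 patients is the wrong number. Neither follows: the primary objective is descriptive, and at 60 to 63 evaluable patients the one-mean precision is only slightly worse than stated.

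**What to change.** Keep 70 patients and change the text in four places.

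1. **Sample size, figures.** Name the formula and the variable with SD 5. Either give the effective size as 63 in total (or 62 in total, 31 per arm), or say that 60 is the target and 70 a rounded-up enrolment. Restate the sampling error at that number (about 1.04 to 1.08 if the one-mean formula was used).
2. **Sample size, scope.** Add: *The number of patients was not chosen to compare recurrence or five-year survival between the groups.*
3. **Study objectives and Trial design.** Replace the two sentences that promise an answer with, for example: *As an exploratory objective, differences between the groups in recurrence and five-year survival will be estimated with two-sided 95% confidence intervals. A non-significant result will not be read as no effect.*
4. **Statistic analysis.** Replace the unspecified method with the same wording, based on Kaplan-Meier estimates so that patients lost to follow-up are censored.

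This needs no extra patients, visits or data. The cost is a more modest conclusion on prognosis and a slightly less favourable stated precision. If the sponsor prefers a confirmatory comparison, it must be sized from stated rates. For an assumed 80% vs 90% with 80% power, the unpooled formula gives about 155 per arm one-sided or 197 two-sided, against 35 planned.

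### The stated sampling error of 1.0 needs 68 evaluable patients on the plan's own one-tailed inputs; the 60 it names give 1.06, and 10% dropout from 70 leaves 63, not 60.

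*Combined protocol and SAP*

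**What the plan says.** All the numbers stand in the Sample size section of the combined protocol and SAP. The spread comes from a previous study, "in which the standard deviation was 5"; the variable it belongs to is not named. The error terms follow: "We assumed an one-tailed α error of 0.05 and a sampling error of 1.0". Enrolment is then fixed: "We propose to enroll 70 participants including 35 patients in the control group and the others in the experimental group". The sentence ends by saying that the plan will "allow for a dropout rate of 10% for an effective sample size of 60".

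The section gives no formula, power, effect size or definition of sampling error. The Statistic analysis section says that "the level of statistical significance was set at" P < 0.05, without saying one-sided or two-sided. It plans a multiple linear regression, a chi test for the coincidence rate and an unspecified method for the follow-up data.

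**The concern.** A sample-size statement should let the reader go from the inputs to the number of patients who will contribute data. Here the inputs lead to a number close to the 70 enrolled, not to the 60 that the plan expects to analyse. Dropout allowance is normally added to the requirement; here it seems to have been taken away from it. Separately, the dropout rate, the enrolled number and the effective number do not agree with one another.

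The sampling error of 1.0 is the only quantitative justification the plan gives for its size. If the evaluable sample does not deliver it, the plan claims a property that the design lacks. Sidedness adds to the uncertainty: one tail is declared for the sample size and nothing is declared for the analysis, so a reader cannot tell which margin applies to the results.

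**Working it through.** **Inputs, all from the Sample size section:** SD = 5; one-tailed α = 0.05, so z = 1.645; error E = 1.0; enrolled 70; dropout 10%; evaluable 60.

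**1. Trying to reproduce the plan's figure.** For the precision of one mean, n = (z × SD / E)².
- One-tailed: (1.645 × 5 / 1.0)² = 67.6, so 68. With the t distribution, 70.
- This is within two patients of the enrolled 70 and eight above the stated effective 60.
- For 60 patients to give 1.0, the SD would have to be √60 / 1.645 = 4.71, not 5.

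**2. Other readings of the inputs.** None gives 60 or 70.
- Two-sided 95% margin for one mean: (1.96 × 5 / 1.0)² = 96.04, so 97 (99 by t).
- Sampling error read as a standard error: (5 / 1.0)² = 25.
- One-tailed margin of 1.0 for a difference between two groups: 2 × 67.6 = 135.3, so 136 per group.
- Two-sample test of a difference of 1.0, one-sided, 80% power: 310 per group.

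**3. Dropout arithmetic.**
- 70 × 0.90 = 63, not 60.
- 60 out of 70 means a loss of 10 / 70 = 14.3%.
- 60 / 0.90 = 66.7, so 67 enrolled would leave 60 at 10% loss.
- 68 / 0.90 = 75.6, so 76 enrolled would leave the required 68.

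**4. Precision achieved, error = quantile × 5 / √n.**

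| Evaluable n | One-tailed 5%, z | One-tailed 5%, t | Two-sided 95%, z | Two-sided 95%, t |
|---|---|---|---|---|
| 60 | 1.06 | 1.08 | 1.27 | 1.29 |
| 63 | 1.04 | 1.05 | 1.23 | 1.26 |
| 68 | 0.997 | 1.01 | 1.19 | 1.21 |
| 70 | 0.98 | 0.996 | 1.17 | 1.19 |

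Worked example at 60: 1.645 × 5 / √60 = 1.062; 1.96 × 5 / √60 = 1.265.

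On the one-tailed terms declared, 1.0 is reached only with almost no loss: 68 of the 70 must be evaluable by z, and all 70 by t. At 60, a bound of 1.0 carries a one-tailed error of 1 − Φ(√60 / 5) = 6.1% instead of 5%.

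The two-sided columns apply only if the analysis is two-sided at 5%, which is an assumption.

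**The case against.** **The formula is inferred.** The plan prints none and does not define sampling error. Read as a standard error, 60 patients give 5 / √60 = 0.65 and the target is met comfortably. This reading is weak: α would then have no role, although the plan states it in the same sentence, and the requirement would be 25, unrelated to 60 or 70. The inference stands as the best available, but it remains an inference. So does the explanation that dropout was taken off the requirement.

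**The 60 may be a rounded floor.** Sixty evaluable at 10% loss needs 67, which could have been rounded up to 70. That would explain the enrolment figure, but not the 60, which the inputs do not produce.

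**The shortfall is small.** On the declared one-tailed terms it is 4% at 63 and 6% at 60, and full retention meets the target. Intervals and P values from the trial will use the observed SD and n, so the planned 1.0 will not itself distort the results. Both points stand and limit the severity.

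**A stronger reading is tempting.** A reader might infer that the analysis requires a two-sided 95% interval, that 1.645 was therefore misapplied, and that the true margin is 1.27, some 27% wider than stated. The documents do not support this. One tail is declared openly, and 1.645 is the correct quantile for a one-sided 5% bound. The Statistic analysis section states no sidedness and plans no interval for a single mean. Two-sided testing is the usual convention and no directional hypothesis is given, so the two-sided figures are worth showing, but only as conditional.

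**Conclusion.** The point holds in a limited form. On the apparent one-sample formula, the plan's inputs need 68 evaluable patients (70 by t), and neither the stated 60 nor the 63 that 10% dropout would leave delivers the stated 1.0. The mismatch between 10% dropout and 60 evaluable is plain arithmetic and needs no assumption about the formula. The shortfall in precision does rest on reading sampling error as the margin z × SD / √n. The two-sided half-widths rest on the further assumption of a two-sided 5% analysis.

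Severity is moderate: the sample-size statement is wrong as written and cheap to correct, but the one-tailed error is off by only a few per cent. Nor should a reader conclude that correcting it validates the trial's size. The calculation concerns one mean of an unnamed variable; it does not address the coincidence rate or the comparison of 35 with 35 for recurrence and five-year survival.

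**What to change.** Keep 70 enrolled and revise the Sample size section as follows.

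- Make the counts agree: either 63 evaluable at 10% dropout, or 60 evaluable at about 14% dropout.
- Name the variable whose SD is 5, define sampling error and print the formula.
- Replace the 1.0 with the precision achieved. Possible wording for the first option: *With an SD of 5 for [variable], 70 enrolled and 63 evaluable after 10% dropout, the one-tailed 5% margin for the mean is about 1.04; the corresponding two-sided 95% half-width is 1.23 to 1.26.* For 60 evaluable, the figures are about 1.06 and 1.27 to 1.29.
- State one sidedness convention, and use it in both the Sample size and the Statistic analysis sections.
- Add that this figure describes a single mean and does not justify the size of the randomized comparison.

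The cost is a few sentences and a less favourable stated precision, with no extra patients. Keeping 1.0 as a firm target would instead mean enrolling 76 one-tailed (68 / 0.90 = 75.6) or 108 two-sided (97 / 0.90 = 107.8), using the z-based requirements. The small one-tailed shortfall does not by itself call for that.

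### Exclusion criterion 1 bars all postmenopausal women, with no definition or reason, while the age range runs to 90 and the conclusions are stated for endometrial carcinoma generally

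*Combined protocol and SAP*

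**What the plan says.** The combined protocol and SAP defines eligibility in two lists.

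- **Inclusion criteria, item 2:** "Females aged 10-90 who are confirmed with endometrial carcinoma and are willing to receive primary non-reserved fertility function surgery".
- **Exclusion criteria, item 1:** "Pregnancy, lactation, postmenopause, or planned pregnancy within two years".

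The research question is worded without any menopausal limit.

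- **Study objectives, primary objective:** "identify the specific number and percentage of pelvic and abdominal lymph nodes that are invaded by metastatic endometrial carcinoma". The second part of that objective concerns agreement between imaging and pathology, again for the disease without restriction.
- **Study objectives, group comparison:** "we plan to find out whether pelvic and abdominal lymphadenectomy would exert positive effect on patients with endometrial carcinoma".
- **Trial design, data source:** "the electronic medical data of patients with endometrial carcinoma will be collected in this study".
- **Trial design, inference:** from recurrence and five-year survival, "the effect of pelvic and peritoneal lymphadenectomy on the prognosis of endometrial carcinoma are drawn".

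Menopause appears nowhere else. The Statistic analysis section lists age among its regression variables, but not menopausal status.

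**The concern.** The women who may enrol and the women about whom conclusions will be drawn are different populations, and nothing in the document connects them.

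This matters most for the primary objective. A percentage of invaded nodes and an agreement rate are descriptive quantities, and they belong to the population that was sampled. Randomisation protects the later comparison of the two surgical groups, but it does nothing for a descriptive percentage. The analysis cannot repair the gap either: adjusting for age supplies no data on a group that was never enrolled.

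The document does not show whether the restriction is intended. If it is deliberate, the randomised comparison stays internally valid and the harm is to generalisability and labelling. If it is accidental, the trial recruits the wrong population for its question.

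The missing definition is a further problem under either reading. The plan does not say how or when menopausal status is established, or whether surgically or medically induced menopause counts. Two investigators could classify the same patient differently.

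**Working it through.** **1. Do the criteria conflict?** The eligible set is females aged 10 to 90 with confirmed disease who accept surgery that does not preserve fertility, minus all postmenopausal women. That set is not empty, so both rules can be followed. But the upper limit of 90 then has little practical effect, because the exclusion has already removed the older part of the range.

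**2. Does the text show intent?** No. The same exclusion also names planned pregnancy, and the Withdrawal section lists pregnancy, although inclusion requires willingness to have surgery that does not preserve fertility. This suggests that the list was not tailored to this trial, but does not prove it. A deliberate restriction remains possible.

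**3. What does the trial estimate, and what does it claim?** The plan gives no figure on this point, so the gap is written algebraically. Let

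- r0 = the percentage in women who are not postmenopausal;
- r1 = the percentage in postmenopausal women;
- p = the postmenopausal share of the general population (of patients, or of nodes for a per-node percentage);
- d = r1 − r0.

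The general percentage is (1 − p) × r0 + p × r1. The trial as written estimates r0. The gap is therefore

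(1 − p) × r0 + p × r1 − r0 = p × (r1 − r0) = p × d.

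Both p and d are assumptions; the documents give neither.

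| | p = 25% | p = 50% | p = 75% |
|---|---|---|---|
| d = 5 points | 0.25 × 5 = 1.25 | 0.50 × 5 = 2.5 | 0.75 × 5 = 3.75 |
| d = 10 points | 0.25 × 10 = 2.5 | 0.50 × 10 = 5.0 | 0.75 × 10 = 7.5 |

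The gap is zero only if p or d is zero. With 0 of 70 patients postmenopausal by rule, the trial can offer no evidence that d is zero.

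**4. Does the sample size depend on this?** The Sample size section gives a standard deviation of 5, a one-tailed α of 0.05 and a sampling error of 1.0. A one-sample precision formula gives (1.6449 × 5 / 1.0)² = 67.64, rounded up to 68, close to the stated 70. Menopausal status does not enter it, so reconciling the criteria does not by itself change the planned number.

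**The case against.** The strongest reply has five parts.

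- **Exclusions exist to narrow inclusions.** A wide age band cut by an exclusion is untidy but workable, and a restricted estimate that is correctly labelled is not wrong. This is true. But the plan does not label it: every statement of the question refers to the disease without restriction.
- **Other exclusions are also unexplained.** Item 3 bars autoimmune, infectious and digestive diseases and hyperparathyroidism without a reason, and the objective is not restated for them. That is fair. The difference, visible in the text alone, is that none of those conditions empties part of a stated inclusion range.
- **The p × d table is an identity with assumed inputs.** This stands. The table shows how the gap behaves; it is not evidence of its actual size. It also covers percentages only. For recurrence and survival, what matters is whether the effect of lymphadenectomy differs by menopausal status, and that is not quantified here. The finding rests on the text, not on the table.
- **Without a definition, exactly zero postmenopausal patients is not assured.** This also stands. Zero is what the rule requires; borderline patients could be classified differently in practice. That is a further reason to define the term.
- **Enrolment may already have begun.** The plan is dated 2019.02.01 and parts of the Statistic analysis section are in the past tense. The documents do not settle this, so the remedy needs a fallback.

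**Conclusion.** The concern holds. Run exactly as written, the trial enrols no postmenopausal women but states its node percentages, agreement rate and prognostic conclusion for endometrial carcinoma generally. Confidence in this reading of the text is high.

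The numerical consequence is unknown. The range of 1.25 to 7.5 points is conditional on the assumed shares and differences and should be quoted only with them. Whether the fault is one of labelling or of recruiting the wrong population depends on the sponsor's intent, which the documents do not reveal. Both readings require a change. Because the point reaches both parts of the primary objective and cannot be corrected at analysis, it should be settled before enrolment.

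**What to change.** The sponsor should state the intended population and reconcile eligibility, objective and inference in one of two ways.

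- **Option A:** remove postmenopause from item 1 of the Exclusion criteria, so that eligibility agrees with the 10 to 90 range and the stated objective. This changes one word of text, but it also changes who is enrolled. The sponsor should then confirm that the planning standard deviation of 5, taken from a previous study that is not named, suits that population.
- **Option B:** keep the exclusion, give a reason and an operational definition of postmenopause, align the age range with it, and restate the objective and the inference as limited to women who are not postmenopausal. The price is a narrower conclusion.

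The drafting cost of either is a short amendment. If enrolment has already started, the rule actually applied should be documented, the menopausal status of those enrolled recorded, and the conclusions limited accordingly.
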